The risks of having blood drawn include some pain when the needle goes in, and a small risk of bruising and/or infection at that site. Some people will get lightheaded, nauseous, or faint. Approximately 3 teaspoons of blood will be drawn and is not likely to cause lightheadedness, however subjects will be observed after blood draw to be sure they are comfortable with ambulation. Subjects will be encouraged to drink plenty of water prior to the blood draw. Phlebotomy will be performed at the antecubital fossa to minimize pain and bruising. Subjects will be seated during the blood draw to minimize dizziness and any risk of falling. Pressure will be applied to the site after the draw and a band-aid will be applied to minimize the risk of bleeding and infection. Fasting laboratories will be processed at URMC local lab. We require fasting laboratories as the lipid panel can be influenced by food intake and it is routine care to do fasting laboratories of at least 6 hours. Due to known side effects of systemic class of medication we want to screen patients for leucopenia, high lipids, liver or kidney diseases; normal or non-clinical significant labs at baseline are useful to rule out these problems and can be helpful in case we have side effects during the study.

The clinical trial team will receive and review the laboratory results between 24-48 hours.

Risks of Ruxolitinib 1.5% cream

Skin-related side effects of ruxolitinib cream are rare, but have included local irritation, pain, itch, redness, acne, and rash. While other side effects are not expected and have not been seen in other studies of ruxolitinib cream, there is a potential risk of side effects

that have been observed with much higher doses of ruxolitinib when given by mouth. These risks include infection, low blood counts, liver inflammation, elevated cholesterol, dizziness, headache, fatigue, insomnia, diarrhea, and abdominal pain. As with any treatment, there is a small risk of an allergic reaction, though this has not been documented for ruxolitinib cream.

There is a risk of no change or worsening of disease, as would be true with any change in treatment.

FDA approved medication label information, risks include:

- Patients treated with oral JAK inhibitors for inflammatory conditions are at risk for developing serious infections that may lead to hospitalization or death
- Reported infections include:
 - Active tuberculosis (TB), which may present with pulmonary or extrapulmonary disease

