 - Invasive fungal infections (eg, candidiasis, pneumocystosis)
 - Bacterial, viral, and other infections due to opportunistic pathogens
- Avoid use in patients with an active, serious infection, including localized infections
- If a serious infection develops, interrupt therapy until infection is controlled
- Do not resume until the infection is controlled.
- Carefully consider the risks and benefits of treatment before initiating therapy in patients with chronic or recurrent infection
- Closely monitor for developing signs and symptoms of infection during and after treatment

Reproductive Risks

Women of childbearing potential will be counseled to use acceptable birth control methods. Women will not be allowed to participate in this study if they are pregnant, become pregnant, or are nursing an infant.

General Risks

When participating in any research study there is a possibility for invasion of privacy or breach of confidentiality. As with any research study, there may be additional risks that are unknown or unexpected. The subjects are advised to contact their study team with any questions and/or concerns. At that time the study team will determine whether or not any untoward medical occurrence is associated with the study and/or study drug and will be recorded on the Medical History and/or Adverse Event page of the source document.

Adverse Event Reporting

An adverse event (AE) is any observation whether or not considered to be product related, that is unfavorable and unintended and that occurs after any use of an investigational medicinal product.

Any observation of abnormality will be documented on the Adverse event form. The Investigator will document the date of occurrence, severity, resolution, and will assess the relationship of the adverse event to the study drug by assigning a causality assessment. Results from laboratory evaluations which are outside of the laboratory reference range will constitute an adverse event only if the Investigator determines that the result is clinically significant.

Severity will be assessed by the following system:

- Mild: easily tolerated, causing minimal discomfort
- Moderate: sufficiently discomforting to interfere with every day activities
- Severe: prevents normal every day activities

Serious Adverse Events (SAE)

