If more than 5 patients report a greater than moderate local side effect (irritation, worsening of rash, vesicles/bulla etc) or if the clinical dermatological score in the treatment area as assessed by the clinician has worsened by more than 50% from baseline in more than 5 patients, then all patients will stop medication until further review and changes made to the protocol. If any unanticipated serious adverse effects are noted all subjects will be notified and changes will be made to future protocols and submitted for approval.

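### The Stopping Criteria halt all treatment for local reactions but state no action on current treatment for a serious event, and their fixed counts cannot be reached in the first five patients

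*Combined protocol and SAP*

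**What the plan says.** The Stopping Criteria in section 5 of the combined protocol and SAP consist of two sentences with three limbs.

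- Local reactions: "If more than 5 patients report a greater than moderate local side effect".
- Score worsening, joined to the first limb by *or*: the clinician-assessed score in the treated area "has worsened by more than 50% from baseline in more than 5 patients". The score is not named.
- Consequence of either count limb: "all patients will stop medication until further review and changes made to the protocol".
- Serious events: "If any unanticipated serious adverse effects are noted all subjects will be notified and changes will be made to future protocols and submitted for approval".

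No denominator, review time point, rationale or trigger probability accompanies the counts.

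Other text bears on the same question:

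- Adverse Event Reporting (section 5) grades severity as mild, moderate or severe, so anything above moderate is severe.
- Risks of Ruxolitinib 1.5% cream (section 5) says "Skin-related side effects of ruxolitinib cream are rare". It also lists low blood counts and liver inflammation seen with oral dosing. Under label information it lists serious, tuberculous and opportunistic infections, with the line "If a serious infection develops, interrupt therapy until infection is controlled".
- Serious Adverse Events and SAE Reporting (section 5) requires every serious adverse event to reach the drug supplier within 24 hours and the IRB in about 3 working days. The investigator assesses the case and consults the supplier.
- The Protocol Summary and section 3 allow up to 25 enrolled, with 15 completing.

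**The concern.** The two sentences treat the more serious situation more weakly. Enough severe local reactions stop everyone's medication, pending review and a change to this protocol. An unanticipated life-threatening event leads, as written, to notification and a change to future protocols, with no statement about the treatment that current participants are still applying. A serious event of a kind the protocol already lists is, on a plain reading, anticipated, so the sentence does not reach it.

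The count limbs raise a separate issue. A fixed number of patients stands for a different level of harm depending on how many have been treated, and it cannot respond to an early cluster. In a single-site, open-label trial for which the documents name no independent safety reviewer, the written rule is what the site would follow.

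**Working it through.** **Step 1. Set the limbs side by side.**

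| Limb | Trigger | Stated action on treatment in this trial | What is changed |
|---|---|---|---|
| Local reaction | severe, more than 5 patients | all patients stop, pending review | the protocol |
| Score worsening | above 50%, more than 5 patients | all patients stop, pending review | the protocol |
| Serious event, unanticipated | any | none stated; all subjects notified | future protocols |
| Serious event, of a listed kind | not covered | none stated | none stated |

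**Step 2. Look for a study-level rule elsewhere.** The 24-hour report to the supplier and the IRB notice apply to all serious adverse events, but they are reporting duties. Case assessment, supplier consultation and the label line on serious infection concern the individual case or patient. Data Monitoring in section 6 permits emergency deviations to protect subjects and sends amendments to the IRB. None of these says what happens to treatment across the trial after a serious event.

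**Step 3. The count.** The plan gives a bare threshold, so there is no figure of its own to reproduce. More than 5 means at least 6. The smallest proportion that triggers either limb is 6/n:

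- n = 5: cannot trigger, even if all five are affected
- n = 6: 6/6 = 100%
- n = 10: 6/10 = 60%
- n = 15: 6/15 = 40%
- n = 25: 6/25 = 24%

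**Step 4. Trigger probability, local-reaction limb alone.** With n treated and true severe rate p, P(X ≥ 6) = 1 − Σ C(n,k) p^k (1−p)^(n−k), summed over k = 0 to 5. The documents give no value for p, so the rates below are assumptions. Example, n = 15 and p = 0.20: the six terms are 0.0352, 0.1319, 0.2309, 0.2501, 0.1876 and 0.1032. They sum to 0.9389, so P = 0.061.

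| Assumed true rate | n = 10 | n = 15 | n = 25 |
|---|---|---|---|
| 10% | 0.000 | 0.002 | 0.033 |
| 20% | 0.006 | 0.061 | 0.383 |
| 30% | 0.047 | 0.278 | 0.806 |
| 40% | 0.166 | 0.597 | 0.971 |
| 50% | 0.377 | 0.849 | 0.998 |

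These are lower bounds for the whole rule, because the score-worsening limb can also trigger it.

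**Step 5. The unnamed score.** If it is the IGA (five levels, coding 0 to 4 assumed, entry at 2 or above per section 3), then 3 to 4 is 1/3 = 33%, 2 to 3 is 1/2 = exactly 50% and so not above it, and 4 cannot worsen. Only 2 to 4 (100%) would count. If HECSI is meant, the limb behaves differently. The text does not say which.

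**The case against.** A reader might infer that the stopping text cannot protect current participants at all. The documents do not support that. Once 6 patients are affected, either count limb stops everyone, and with 25 treated and an assumed rate of 30% the local limb alone acts with probability 0.806. The serious-event sentence also notifies all current subjects.

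A reader might also infer that a listed serious risk triggers nothing. That goes too far as well. Section 5 sends every serious adverse event, anticipated or not, to the supplier and the IRB. It also names an unusual frequency of non-serious events as a reason to consult the supplier, which covers part of the early-cluster scenario.

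Three further points stand in the plan's favour:

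- The label line on interrupting therapy is a patient-level statement, so its absence from a study-level rule is not a contradiction.
- The reference to future protocols may be loose drafting for later versions of this one, since the changes are to be submitted for approval.
- A limit well above a rate described as rare is not in itself an error. The limb also counts worsening of rash, which may be the disease, and the protocol acknowledges that risk separately.

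Fifteen treated is also the least favourable case. It is the completer target, reached with no dropouts, and patients who discontinue still count towards the 6. Five of the first five is an extreme pattern: at a 30% rate its probability is 0.3^5 = 0.002.

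What survives is the serious-event sentence. Neither the reporting duties nor a charitable reading of the wording supplies a stated action on treatment in this trial.

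**Conclusion.** The concern holds as an inconsistency within the Stopping Criteria, not as an absence of protection. Followed as written, the rule is weaker for a serious event than for local irritation: no limb states an action on current treatment for any serious event, and listed serious risks fall outside the only limb that mentions serious events. This rests on reading *unanticipated* and the reference to future protocols in their ordinary sense. The reporting and consultation duties reduce the consequence without closing the gap.

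The count limbs cannot act in the first five patients, and the proportion they need falls from 100% at 6 treated to 24% at 25. The probabilities depend on assumed rates and cover one limb only. A fixed count rather than a running proportion is a design choice that can be defended. The shortcoming is that no rationale or trigger probability is given and that the score is not identified.

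**What to change.** The sponsor and IRB should reconcile the serious-event sentence of the Stopping Criteria with the sentence before it and with the risk and SAE text in section 5. The revised sentence should state what happens in this trial to participants now on treatment, and whether the serious risks that the protocol lists are covered. The reference to future protocols should be replaced or clarified. The same edit should name the score used in the worsening limb and give the rationale for the count, with its trigger probability over the range of patients treated.

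The thresholds and the clinical actions remain for the sponsor and IRB to choose. The cost is protocol wording and, depending on what they choose, a possible short pause for review in a small single-site trial.

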6. DATA ANALYSIS AND DATA MONITORING

Objectives and Endpoints:

Primary objective & outcome:

1. To assess the efficacy of Ruxolitinib cream 1.5% on skin lesions in patients with Chronic Hand Dermatitis:

- proportion of patients achieving an Investigators Global Assessment (IGA) score of 0 or 1 with at least a 2-step improvement (IGA treatment success) at week 12
- HECSI-75% from baseline to week 12

Secondary objective & outcome:

1. To assess the efficacy of Ruxolitinib cream 1.5% on other clinical domains (e.g. pruritus, pain, work productivity and activity impairment; daily quality of life index/DLQI, Hand Eczema Severity Index/HESI):

- Time to IGA treatment success
- Change in HECSI score from baseline to week 4, 8 and 12.
- Proportion of subjects with a ≥ 2 and ≥ 4 -point improvement in Itch Numerical Rating Scale (NRS) score from baseline to week 4, 8 and 12.
- HECSI-75% at week 8
- HECSI-90% at week 12

2. To assess safety and tolerability of Ruxolitinib cream 1.5% in patients with chronic hand dermatitis:

- Incidence, frequency and severity of adverse events and laboratory data for hematology, serum chemistry and urinalysis
- use of rescue medications

Exploratory objective & outcome:

1. To assess the effect of Ruxolitinib cream 1.5% on patient reported outcomes

- Change from baseline to week 4, 8 and 12 in DLQI

- Change from baseline to week 4, 8 and 12 in work productivity and activity impairment index
2. To assess the efficacy of Ruxolitinib cream 1.5% on skin barrier integrity in patients with Chronic Hand Dermatitis:
- change in transepidermal water loss (TEWL) and barrier integrity score (TEWL recovery after tape stripping) and pH from baseline to week 4 and end of treatment on perilesion (normal appearing) skin
3. To identify translational skin biomarkers
- change in the expression of selected biomarkers in skin samples obtained from tape stripping (d-squame) at baseline and end of treatment (week 12)
4. To identify change in microbiome after treatment

Side effects and baseline characteristics will be tabulated qualitatively. The blinded pre- vs post evaluation will be analyzed for IGA scores by the Wilcoxon sign-rank test.

Data Storage and Confidentiality

All data from the clinical trial will be securely stored using the REDCap. Only the minimal necessary data is being collected. This includes: name, contact information, age, sex, MRN, history of allergies, dermatologic diagnosis, history of other medical conditions, current medications and clinical scores. Subjects may be asked to sign an Authorization for Release/Disclosure of Medical Health Information form if a chart is not established at the University of Rochester. Access to this protected health information will be restricted to the principal investigator, sub-investigator and study coordinators. Information obtained will be stored in REDcap. Samples will be assigned unique identifiers and stored separately from the key linking the sample to the identifiers. The electronic key will be stored in REDcap file, accessible only to study personnel. Any paper documents containing identifiers will be kept in a binder in a locked cabinet accessible only to study personnel.

Data Monitoring

The study will be monitored in compliance with the relevant parts of 21 CFR and according to the ICH GCP Guidelines.

Case Report Forms will be completed as information becomes available or within five days of a Study Visit.

The Principal Investigator or a Sub-investigator will sign and date the indicated places of the Case Report Form. This signature will indicate that thorough inspection of the data therein has been made and will thereby certify the contents of the form.

The procedures outlined in the protocol and case report forms will be carefully reviewed by the Sponsor, Investigator and staff prior to Study Initiation to ensure appropriate interpretation and implementation. No deviations from the protocol shall be made except

in emergency situations where alternative treatment is necessary for the protection, proper care and well-being of subjects.

Amendments will be submitted to the IRB for their review and approval prior to implementation. When an amendment to a protocol substantially alters the study design or increases potential risk to the study subject, the Informed Consent form will be revised and if applicable, subject's consent to continue participation will again be obtained.

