1. PROTOCOL SUMMARY

Title: Topical Ruxolitinib (Jak1/Jak2 inhibitor) in Chronic Hand Dermatitis attenuates inflammation and enhances skin barrier repair.

Principal Investigator: [name] [name];
[contact]

Single site: Department of Dermatology - University of Rochester Medical Center, Rochester, NY

Study phase: Open label, proof of concept study

Population: Females and Male, age 18 - 75 years, who have moderate to severe Chronic Hand Dermatitis (CHD)

Number of participants: Up to 25 will be enrolled with 15 completing full study term

Intervention: Ruxolitinib cream 1.5% is an investigational drug that will be applied twice daily (BID) for 12 weeks (IND exempt) by the study participant. Ruxolitinib (Other Name: INCB018424) cream is a topical formulation applied as a thin film to affected areas.

Objectives and Endpoints:Primary objective & outcome:

1. To assess the efficacy of Ruxolitinib cream 1.5% on skin lesions in patients with Chronic Hand Dermatitis:

- proportion of patients achieving an Investigators Global Assessment (IGA) score of 0 or 1 with at least a 2-step improvement (IGA treatment success) at week 12
- Hand Eczema Severity Index (HECSI)-75% from baseline to week 12

Secondary objective & outcome:

- To assess the efficacy of Ruxolitinib cream 1.5% on other clinical domains:
Time to IGA treatment success
- Change in HECSI score from baseline to week 4, 8 and 12.
- Proportion of subjects with a ≥ 2 and ≥ 4 -point improvement in Itch Numerical Rating Scale (NRS) score from baseline to week 12.
- HECSI-75% at week 8
- HECSI-90% at week 12

2. To assess safety and tolerability of Ruxolitinib cream 1.5% in patients with chronic hand dermatitis:

- incidence, frequency and severity of adverse events and laboratory data for hematology, serum chemistry and urinalysis
- use of rescue medications

Exploratory objective & outcome:

1. To assess the effect of Ruxolitinib cream 1.5% on patient reported outcomes
 - Change from baseline to week 4, 8 and 12 in DLQI
 - Change from baseline to week 4, 8 and 12 in work productivity and activity impairment index
2. To assess the efficacy of Ruxolitinib cream 1.5% on skin barrier integrity in patients with Chronic Hand Dermatitis:
 - change in transepidermal water loss (TEWL) and barrier integrity score (TEWL recovery after tape stripping) and pH from baseline to week 4 and end of treatment on perilesion (normal appearing) skin
3. To identify translational skin biomarkers

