Subjects will apply topical Ruxolitinib 1.5% cream twice a day for 12 weeks on eczematous areas of hands and adjoining clinically normal (perilesional) area. We included non-lesional/perilesional skin to evaluate the safety (e.g. irritant or toxic effects) of the compound on irritated/atopic skin, as those subjects have a lower irritancy threshold^{vi}. Also, skin barrier impairment (e.g. increase water loss/TEWL) can be already detected in normal appearing skin in atopic subjects and it is thought to allow penetration of haptens/allergens/irritants with consequent activation of an inflammatory response. It is our hypothesis that treatment with topical Ruxolitinib, a JAK1/JAK2 inhibitor, will normalize skin barrier integrity in perilesion skin. During the study, subjects will be allowed to stay on bland moisturizer and anti-histamine on a stabilized dose and expected to maintain this dose throughout the study. **In addition to clinical and safety outcomes**, the study design will include **exploratory** mechanistic outcomes, in a stepwise tactic. During the trial we will collect: 1) non-invasive skin barrier assessment (i.e. TEWL, SC integrity score); 2) stratum corneum extract to investigate potential biomarkers and skin microbiome (stored for future investigation); 3) Patient oriented outcomes. If the data gathered from the clinical trial demonstrates the clinical improvement we expect, the mechanistic studies will be extremely relevant to start clarifying specific target downstream to Ruxolitinib efficacy in CHD as well as biomarkers that could eventually be investigated in consequent larger clinical trials.

ADMINISTRATIVE ORGANIZATION

UR Dermatology at College Town is the only participating site in this research study.

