3. STUDY POPULATION

Number of patients: Up to 25 total subjects. We might need to enroll additional subjects in case of subject early discontinuation to reach the total number of 15 evaluable subjects (complete data set).

Study population: Females and Male, age 18-75 years, who have Chronic Hand Dermatitis

Racial and Ethnic Origin: We will not have any restrictions based on racial or ethnic origin. We based our target research population racial and ethnic distribution on the data of the 2000 United States Census for the Monroe County Area.

Vulnerable subjects: We will not be targeting vulnerable subjects

Inclusion Criteria:

- Age 18-75 years.
- Diagnosis of chronic hand eczema defined as hand eczema, which has persisted for more than 3 months or returned twice or more within the last 12 months.
- Disease severity graded as moderate to severe according to IGA (i.e., IGA ≥ 2).
- Recent history (within 1 year before the screening visit) of inadequate response to topical corticosteroid and/or calcineurin inhibitors treatment or topical corticosteroid treatment being medically inadvisable.

Exclusion Criteria:

- Active atopic dermatitis in regions other than the hands requiring medical treatment.
- Active psoriasis in regions other than the hands requiring medical treatment.
- Clinically significant infection (e.g., impetiginized hand eczema or tinea manuum) on the hands.
- Patients with excessive contact of hands with water (longer than 2 hours a day; or > 20 hands washing at day) that is believed to be a predominant cause of the hand dermatitis.
- Subjects with known antigen sensitization based on Patch test (with 3 years) that are unable to reduce contact with the specific antigen(s).
- Subjects chronically and consistently exposed to known irritant or other substance known to impact skin barrier will be excluded based on PI judgement.
- Systemic treatment with immunosuppressive drugs, immunomodulating drugs, retinoids, or corticosteroids within 4 weeks prior to baseline.
- Systemic treatment with antibiotics within 4 weeks prior to baseline
- Phototherapy on the hands within 4 weeks prior to baseline.
- Use of topical immunomodulators (e.g., phosphodiesterase-4 (PDE-4) inhibitors, pimecrolimus, tacrolimus) or topical corticosteroids on the hands within 2 weeks prior to baseline.
- Use of topical antibiotics on the hands within 2 weeks prior to baseline.

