- **Study Drug Diary:** subjects will be provided with a prepopulated dated calendar to record their twice daily (AM and PM) application of study medication as well as the time the medication is applied. Also, on this diary the subject can indicate if a missed dose occurred and there is a blank space they can write in the reason it was missed. At the END of each day the subject will need to indicate on the same study diary their level of hand dermatitis itch throughout the day – 0=no itch and 10=worst imaginable itch. Subjects will indicate their level 0-10 by circling the number that best applies to them for that particular date. Detailed instructions are provided on the Incyte Study Diary as well as contact information of coordinator.

Prohibited Medications and procedures: use of topical or systemic immunosuppression/immunomodulators medications and Phototherapy is not permitted during the study. Hand surgery or other procedures (including but not limited to Cryotherapy, ED&C, skin biopsy) are disallowed during the study. If medically necessary, the investigator will withdraw the patients from the study.

5. RISK, BENEFITS and PROTECTION AGAINST RISKS

Risks Associated with Digital Picture

There are no known risks for the digital picture. The image will not include identifying features and will be labeled with study subject ID and date. ~~Pictures will be taken with a dedicated camera, stored on a secure server.~~ Pictures will be taken through the Haiku App and stored in the patients EMR in Epic.

Risks Associated with Barrier Assessments

There are no known risks for the barrier assessments.

Risks Associated with Tape Stripping

The risks associated with tape stripping, theoretically, include the rare possibility of an allergic reaction to the tape and infection. Since the tape is removed immediately after application, the risk of reaction is extremely low. In previous and ongoing studies involving tape stripping, it has been noted that a very mild erythema may develop immediately after a series of tape stripplings on one localized area of skin, presumably due to the mild mechanical disturbance. The erythema is expected to resolve within 12 hours without sequelae. The risk of skin infection is extremely low since only superficial skin layers are removed. Subjects will be provided with wound care information and a department phone number to contact should they have any concerns.

Risks of Phlebotomy

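### The week-12 response rates have no stated denominator, and a rate based on the 15 complete data sets would run high if the subjects who leave are treatment failures

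*Combined protocol and SAP*

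**What the plan says.** All references are to the combined protocol and SAP.

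- **Size and replacement.** Section 1 (Number of participants) plans "Up to 25 will be enrolled with 15 completing full study term". Section 3 (Number of patients) says that more subjects might be enrolled after early discontinuation "to reach the total number of 15 evaluable subjects (complete data set". This is the only place where a set of evaluable subjects is described.
- **Treatment during the study.** Section 2 (Design & Methodology): "subjects will be allowed to stay on bland moisturizer and anti-histamine on a stabilized dose". Section 4 (Prohibited Medications and procedures): "use of topical or systemic immunosuppression/immunomodulators medications and Phototherapy is not permitted during the study". The next sentence of that paragraph bars hand surgery and other hand procedures, and the paragraph ends "If medically necessary, the investigator will withdraw the patients from the study".
- **Emergency deviations.** Section 6 (Data Monitoring) permits departures from the protocol only "in emergency situations where alternative treatment is necessary for the protection, proper care and well-being of subjects".
- **Outcomes and analysis.** Section 6 lists two primary outcomes at week 12: IGA treatment success, as a proportion of patients, and HECSI-75. Under safety and tolerability it lists "use of rescue medications". The one named test is a pre-versus-post comparison that "will be analyzed for IGA scores by the Wilcoxon sign-rank test".

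No section names an analysis set, a denominator for the two responder proportions, a missing-data method, or a rule for how a withdrawn or rescued subject counts.

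**The concern.** A subject whose hands do not improve has no route to stronger treatment inside the study. If other active therapy becomes necessary, the subject is withdrawn, probably without a week-12 score, since nothing provides for one after withdrawal. That subject no longer has a complete data set, and another may be enrolled in the same place. Needing other therapy for hand eczema is itself a sign of treatment failure, so this kind of loss would not be random with respect to response.

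Such losses are plausible here. Section 3 recruits patients with a recent inadequate response to topical corticosteroids or calcineurin inhibitors, or for whom topical corticosteroids are inadvisable, and keeps these drugs off the hands for 2 weeks before baseline. Section 5 names lack of change or worsening as a risk.

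At stake is the main product of the study, its week-12 response rate. There is one arm, so no control group would show the distortion. Treatment is open label and the denominator is not fixed in advance, so it could be settled after the results are known. The harm is an over-optimistic proof-of-concept estimate carried into the larger trials that Section 2 has in mind. It is not a wrong confirmatory decision, because the plan sets no threshold.

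**Working it through.** **Inputs from the plan.** At most 25 enrolled and 15 completing (Section 1); 15 evaluable with complete data (Section 3). There is no sample-size derivation to reproduce and no withdrawal rate. The two figures imply only a ceiling on non-completion: 1 − 15/25 = 40%, or 25 − 15 = 10 subjects.

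**Inputs assumed.** The number of responders among the 15 completers, x (6, 9 or 12), and the number of treated subjects who leave and are replaced, k (2 or 5). Only k = 10 comes from the plan, as its limit.

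**Formula.** The completer rate is x/15. If all k leavers are non-responders, the all-treated rate is x/(15+k). The ratio of the second to the first is 15/(15+k). It does not depend on x, but it does depend on all k being non-responders.

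- k = 2: 15/17 = 0.88
- k = 5: 15/20 = 0.75
- k = 10: 15/25 = 0.60

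**With x = 9 (exact Clopper-Pearson 95% intervals).**

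| k | Rate | 95% interval |
|---|---|---|
| 0 | 9/15 = 60.0% | 32.3 to 83.7 |
| 2 | 9/17 = 52.9% | 27.8 to 77.0 |
| 5 | 9/20 = 45.0% | 23.1 to 68.5 |
| 10 | 9/25 = 36.0% | 18.0 to 57.5 |

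**Overstatement in percentage points, x/15 − x/(15+k).**

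| x | k = 2 | k = 5 | k = 10 |
|---|---|---|---|
| 6 | 4.7 | 10 | 16 |
| 9 | 7.1 | 15 | 24 |
| 12 | 9.4 | 20 | 32 |

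**If only half of the leavers are non-responders** and the rest respond at the completer rate, the all-treated rate is (x + 0.5·k·x/15)/(15+k). With x = 9:

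- k = 2: 9.6/17 = 56.5%, overstated by 3.5 points
- k = 5: 10.5/20 = 52.5%, overstated by 7.5 points
- k = 10: 12/25 = 48.0%, overstated by 12 points

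If nobody leaves, or if leavers respond at the completer rate, the overstatement is zero. The k = 10 case is an extreme: not every non-completer would leave for other therapy, and the 25 enrolled may include screen failures who never applied the drug.

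**The case against.** The strongest reply is that the plan never prescribes a completer analysis. A reader might infer from Section 3 that the responder rates will be computed on the 15 complete data sets only. The documents do not say so: 15 is an enrolment target, and Section 6 speaks only of patients. This stands, and it limits the point to a bias that the plan leaves open. The silence is still not neutral, because the complete data sets are the only analysable population described.

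Three other stronger readings also go beyond the text.

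- *Every leaver is replaced until 15 complete.* Section 3 is permissive and enrolment is capped at 25.
- *Those who leave are treatment failures.* The withdrawal sentence directly follows the one on hand procedures, and a prohibited drug could be needed for another illness. Early discontinuation covers any reason. A complete data set is not defined either: if it includes the week-16 follow-up visit, a week-12 responder could be classed as not evaluable.
- *The Wilcoxon test forces a completer analysis.* It names no week, and clinical scores are scheduled at weeks 4 and 8, so a subject who leaves after week 4 can have a post-treatment IGA. In any case it does not analyse the responder proportions.

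It is also fair to say that 52.9% and 45.0% lie well inside the interval for 9/15, and that no stated decision turns on the rate. That bears on how serious the point is. It does not remove the bias, which a wide interval does not correct.

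Finally, counting every missing score as non-response can push the rate down. That is true, and it is why withdrawal reasons should be tabulated and the complete-data-set rate shown beside it.

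**Conclusion.** The point holds as a risk that the plan leaves open. Withdrawal for medically needed prohibited treatment, optional replacement up to 25 to reach 15 complete data sets, and no stated denominator together allow a week-12 rate that is too high, to the extent that those who leave are treatment failures. The documents do not settle the size, which may be zero. If all k replaced subjects are non-responders, the all-treated rate is 15/(15+k) of the completer rate, with a lower bound of 0.60 at the planned limit of k = 10. The percentages above rest on assumed responder counts and, apart from that limit, assumed numbers of leavers. For a small open-label proof-of-concept study this is a cheap improvement that should be made, and it does not invalidate the design.

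**What to change.** Add to Section 6:

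1. For IGA success and HECSI-75 at week 12, the denominator is all subjects who applied study drug.
2. A subject who received other active hand-eczema therapy before week 12, or was withdrawn for needing it, is a non-responder. So is any subject with no week-12 score.
3. The reason for each withdrawal is recorded and tabulated, so that dropouts unrelated to hand eczema are visible.
4. The rate among complete data sets is shown as a supplementary analysis.

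Scoring week 12 regardless of rescue would not be enough, because Section 4 takes the subject out of the study and no later score is planned.

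The cost is one analysis rule and one data field. Concomitant medications are already reviewed at the visits, but that review captures drugs taken and not drugs needed, so the withdrawal reason has to be added. No extra visits, subjects or procedures are required. The downside is a possibly lower, somewhat conservative response rate.
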